**1. Introduction and Purpose:**

It is standard practice in the United States and many parts of world to perform Gastrointestinal (GI) endoscopy with the patient under deep sedation (1). Obesity is accepted as a patient specific risk factor for hypoxic events during procedural sedation for GI endoscopic procedures. The Obese population has a higher prevalence of obstructive sleep apnea (OSA) which is characterized by repeated obstruction of the upper airway, and leads to apnea and desaturation. This prospective, randomized study was designed to compare the effectiveness of the high flow nasal cannula and the standard nasal cannula in morbidly obese (BMI > 40) patients receiving deep intravenous sedation during colonoscopies. This study will assess whether use of the high flow nasal cannula (HFNC) leads to less intraoperative desaturation events compared to the current standard of care.

**Hypothesis 1-** The HFNC group will have significantly lower incidence of desaturation episodes (SpO2 <90) than the standard nasal cannula group during procedural sedation for colonoscopies.

**Primary objective:** To compare the frequency of desaturation episodes during procedural sedation in obese patients undergoing colonoscopies.

**Hypothesis 2-** The HFNC group will require fewer interventions to treat hypoxic events than the standard nasal cannula group during procedural sedation for colonoscopies.

**Secondary objective1:** To compare the number of interventions made by the anesthesia providers required to treat desaturation events during procedural sedation in patient undergoing colonoscopies.

**Hypothesis 3-** Use of HFNC would decrease sedation-related adverse events in obese subjects with OSA.

**Secondary objective2:** To determine the frequency of desaturation episodes during procedural sedation in obese patients with undiagnosed OSA.

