## 8. Sources of Research Material:

- Subjects undergoing colonoscopy
- Electronic Medical Record
- Anesthesia Reports
- PHI including name, medical record number, contact information including demographic information including age, gender, race, birth date, weight, height, BMI and medical and surgical history, medication list, ASA classification.
- **Procedural sedation-related variables:** type of sedation agent used for procedural sedation, propofol dose, propofol infusion time, opioid use, any other combination agent for the procedural sedation during colonoscopy, Procedure time, premature termination of procedure.
- **Respiratory event-related variables;** Anesthesiologist intervention (intubation, airway repositioning, Chin lift); Type of airway used (oral airway, nasal airway, bag mask ventilation, suctioning), Laryngospasm or any other airway obstruction; pulse oximetry reading, the number and duration of apnea/hypoxia episodes.
- **Hemodynamic variables** such as baseline blood pressure
- **Postoperative Recovery:** Aldrete score in recovery, the time spend in PACU
- Unplanned hospital admission

- Stop Bang questionnaire for OSA screening

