### **14. Biostatistics:**

The study is powered to detect a 50% reduction in the frequency of desaturation episodes in patients with HFNC compared to patients using a standard nasal cannula. Quadeer et al. (3) reported a 51% incidence rate for desaturation episodes below 90% in patients with standard nasal cannula. Thus to detect a difference of 25% with 80% power and a type 1 error rate of 0.05, the study would need a sample of 59 per group (total n = 118). Assuming a 10% loss of subjects, the total sample size to be enrolled is 130. An interim analysis will be performed at 50% of the enrolment. Based on the interim analysis results, study may be stopped for futility if there is no difference in interim analysis or for early termination for effectiveness if the observed difference at the time is large enough. Obrien-Flemming  $\alpha$ -spending function approach would be used to develop acceptance or rejection boundaries. Continuous data will be summarized using means and standard deviations and categorical data will be summarized using frequencies and percentages. The proportions of desaturation episodes below 90% in the two groups will be compared using a Z test or Fisher's exact test. Mean durations of desaturation episodes and mean numbers of interventions to treat hypoxic events in the two groups will be compared using Student's t-tests or Wilcoxon-Mann-Whitney tests. Frequencies of sedation-related adverse events will be compared using chi-square tests or Fisher's exact tests. Normality of the sample data will be assessed using normal quantile plots. Level of significance will be set at 0.05 and Bonferroni corrections will be made for all primary hypotheses tests.

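### The unadjusted primary test is valid, but it leaves out the STOP-BANG randomisation stratum and the BMI already collected; prespecifying both could gain a few points of power at almost no cost

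*Combined protocol and SAP*

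**What the plan says.** Section 14 (Biostatistics) gives one primary test: "The proportions of desaturation episodes below 90% in the two groups will be compared using a Z test or" Fisher's exact test. No regression, stratified or covariate-adjusted analysis appears anywhere in the document.

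Section 3 (Concise Summary of Project) classifies subjects by STOP-BANG score, 5 or more versus 4 or fewer, and randomises within those strata. Section 14 does not mention the stratum again.

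Section 8 (Sources of Research Material) lists "demographic information including age, gender, race, birth date, weight, height, BMI and medical and surgical history" among the data collected. Section 6 admits only morbidly obese subjects, with BMI from 40 upwards. Section 1 gives the reason for expecting BMI to matter: "Obesity is accepted as a patient specific risk factor for hypoxic events during procedural sedation for GI endoscopic procedures".

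On saturation, section 3 describes charting each minute while the anesthetic is running, and puts the cannula on 5 minutes before the anesthetic starts. Section 8 lists pulse oximetry under respiratory-event variables. No reading before cannula placement is named.

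**The concern.** A factor chosen for stratification is one the investigators expect to predict outcome. If it does, a test that ignores it is somewhat conservative, because the design has removed between-arm variation that the crude standard error still counts. BMI is not a stratification factor, so a chance difference between arms of 59 can shift the single reported estimate. Adjusting for such a difference only after seeing it would be a data-driven choice, so adjustment has to be specified beforehand.

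The planned size leaves little slack: it gives 80.5% power on its own assumptions. Precision available from data already in hand is therefore worth a sentence in the plan.

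**Working it through.** **Inputs from section 14.** Control rate 0.51 ("reported a 51% incidence rate for desaturation episodes below 90% in patients with standard nasal cannula"); difference, power and alpha ("Thus to detect a difference of 25% with 80% power and a type 1 error rate of 0.05"), so 0.51 v 0.26; size ("the study would need a sample of 59 per group (total n = 118"). I read the endpoint as the proportion of subjects with at least one SpO2 below 90%, which is how the sample size treats it.

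**Plan's figure.** Two-sided, pooled variance, mean rate 0.385:

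n = [1.960 × √(2 × 0.385 × 0.615) + 0.842 × √(0.51 × 0.49 + 0.26 × 0.74)]² / 0.25² = (1.349 + 0.560)² / 0.0625 = 58.3, so 59 per group. This reproduces the plan. Power at 59 per group is 80.5%.

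**Approximate gain from adjustment.** If covariates explain a fraction R² of the outcome variance, the effective size is 59/(1 − R²). The documents give no R², so these values are assumptions:

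| R² | 0 | 0.02 | 0.05 | 0.10 | 0.20 |
|---|---|---|---|---|---|
| Power, % | 80.5 | 81.3 | 82.5 | 84.5 | 88.5 |

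**Simulation of the proposed model.** Logistic regression on arm, stratum and one standard-normal covariate standing for BMI; 59 per arm; marginal rates held at 0.51 and 0.26; strata split 50/50 and balanced between arms (an assumption); 6,000 trials per row; critical value 1.96. Power in %:

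| Stratum OR | BMI OR per SD | Crude Z | Wald | Score | Likelihood ratio |
|---|---|---|---|---|---|
| 1 | 1 | 80.4 | 80.4 | 80.8 | 80.9 |
| 1.5 | 1.25 | 79.8 | 80.6 | 81.0 | 81.2 |
| 2 | 1.25 | 80.9 | 81.8 | 82.3 | 82.6 |
| 3 | 1.25 | 81.0 | 83.1 | 83.6 | 83.8 |
| 3 | 2.0 | 80.9 | 85.8 | 86.3 | 86.4 |

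The Monte Carlo standard error of each entry is √(0.8 × 0.2/6000) = 0.5 points. In the last two rows, Wald and score power lies about 3 to 6 points above the planned 80.5%, or 2 to 5 points above the crude test on the same data.

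**Type I error, final look.** With 51% in both arms, the crude test gave 4.4–5.3%, Wald 4.6–5.5%, score 4.7–5.6% and likelihood ratio 4.8–5.8% (standard error about 0.3). Other runs put the likelihood-ratio test as high as 6.0%. With a strong stratum effect the crude test is conservative: 4.5% at a stratum odds ratio of 3 and 3.5% at 5, against 5.1% and 5.2% for a stratified Cochran-Mantel-Haenszel (CMH) test.

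**Type I error, interim.** About 30 per arm; assumed boundary |z| > 2.963 (nominal 0.31%); 15,000 null trials per setting at 38.5% in both arms. Crude 0.22–0.31%, Wald 0.16–0.23%, score 0.32–0.33%, CMH 0.28%, likelihood ratio 0.41–0.47%. A test built on the standardised risk difference and its large-sample standard error gave 0.49–0.61%.

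**Chance imbalance.** The difference between arms in a standardised covariate has SD √(2/59) = 0.18, so a 95% range of ±0.36 SD. The shift in the risk difference is about imbalance × log(OR) × mean p(1 − p). At 0.36 SD and OR 2.0 this is 0.36 × 0.693 × 0.200 = 5.0 points; at OR 1.25, 0.36 × 0.223 × 0.218, or just under 2 points. The crude standard error is √(0.51 × 0.49/59 + 0.26 × 0.74/59) = 8.7 points.

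**Events available.** 59 × (0.51 + 0.26) = 45 at the final look and 30 × 0.77 = 23 at the interim, for three terms.

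**The case against.** The strongest reply is that nothing is broken. Randomisation protects the crude test, its standard error already allows for chance imbalance, and STOP-BANG is balanced by design. All of that stands. A reader might infer that the unadjusted test is biased or invalid; the simulations show no inflation of its type I error.

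Three other tempting readings also go beyond the documents.

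- *That a pre-cannula SpO2 is already in hand as a covariate.* The charting described begins after the cannula is on. Section 4 lists monitors before cannulas, so a reading could be taken, but the plan does not say that it is recorded. A reading under the cannula is affected by treatment and unsuitable for adjustment.
- *That the protocol shows rising BMI driving desaturation in this population.* Section 1 speaks of obesity in general, and the study cited in section 2 contrasts BMI above 30 with non-obese patients. Neither speaks to variation above 40, the only range enrolled. BMI alone may add almost nothing.
- *That power is certainly being lost.* Gains to the mid or upper 80s need strong assumed effects. For a single covariate with an odds ratio of 1.25 per SD, logistic power was 80.6% against 80.0%.

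The objection that adjustment has a cost at the interim is partly right: with about 23 events the likelihood-ratio test is liberal. A score, Wald or CMH test avoids this. What remains is an uneven trade, with a possible gain and almost no loss.

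**Conclusion.** The concern holds as a modest efficiency point. The stratum used in randomisation and a collected baseline variable are both absent from the primary analysis, and including them is worthwhile. The expected gain is about 0 to 2 points of power over 80.5% if they are weak predictors. It is about 3 to 6 points at a stratum odds ratio of 3 with BMI odds ratios of 1.25 to 2.0 per SD, and essentially nil, without loss, if they predict nothing. These strengths and the even split between strata are assumptions; the documents supply neither. The omission of the stratum is the better-supported half of the point, since the protocol itself selected that factor. The trial's conclusions would not be invalid if the plan stayed as it is.

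**What to change.** In section 14, before any comparative data are seen:

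1. Define the primary analysis as logistic regression of any SpO2 below 90% (yes/no per subject) on arm, STOP-BANG stratum (5 or more v 4 or fewer) and continuous BMI.
2. Report the standardised risk difference with 95% CI.
3. Name one test statistic for the O'Brien-Fleming boundaries: the model's Wald or score test at both looks, or a CMH test stratified by STOP-BANG at the interim. The score test stayed closest to nominal at the interim here. Do not use the likelihood-ratio test, and do not base the interim decision on the large-sample interval for the risk difference.
4. Keep a single named crude test as supportive. The present choice is open, and it matters: Fisher's exact test has 74.9% power at 59 per group, against 80.5% for the Z test.
5. Leave SpO2 out unless a pre-cannula reading is defined and recorded for every subject from the start of the trial. Do not adjust for propofol dose or procedure time, which arise after randomisation.

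Items 1 to 4 cost SAP wording only, with no change to sample size or procedures. The price is a slightly more complex model to report. Adding a pre-cannula SpO2 would also need a change to data collection.

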All patients will receive a similar intravenous anesthetic with a propofol infusion titrated to a Richmond Agitation-Sedation Scale (RASS) score of 3-4. A lidocaine bolus of up to 100 mg can be used prior to the start of the propofol infusion for initial tolerance of the drug. Patient saturation is recorded every minute during the anesthetic on the electronic medical record and is available for review. The duration and frequency of all measurements at or below 90% will be recorded by the Electronic Medical Record (EMR). The anesthesia providers will be instructed to intervene only when the patient's saturation falls below 90%, by either manually performing a jaw thrust, placing a nasal or oral airway, bag mask ventilation, increasing the patients FiO2 or decreasing the rate/ pausing the propofol infusion or endotracheal intubation. They will be instructed to write a quick note at the time of intervention in the EMR describing their maneuver. Duration of the study will be the length of the procedure through discharge from the Postoperative Anesthesia Care Unit (PACU).

Our hypothesis is that the patients in the high flow nasal cannula group will experience a marked reduction in intraoperative desaturation events as compared to the Salter cannula group.

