#### **Outcome Measures:**

- Lowest recorded saturation
- The frequency of desaturation episodes (SpO2 <90%)
- Duration of desaturation episodes (SpO2 <90%)
- Number of apnea episodes
- Dose of propofol or other combination for sedation during colonoscopy
- Anesthesiologist intervention (intubation, airway repositioning, Chin lift)
- Type of airway used (oral airway, nasal airway, bag mask ventilation, suctioning)
- Premature termination of procedure
- Unplanned hospital admission

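### Section 14 tests desaturation duration without defining the unit or the value for patients with no episode; on the ordinary reading it compares about 30 Salter with 15 HFNC patients selected after randomisation

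*Combined protocol and SAP*

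**What the plan says.** Section 14 (Biostatistics) says: "Mean durations of desaturation episodes and mean numbers of interventions to treat hypoxic events in the two groups will be compared using Student's t-tests", with Wilcoxon-Mann-Whitney as the alternative. The Outcome Measures list in Section 3 includes the duration of desaturation episodes, defined by saturation under 90%. Section 8 collects "the number and duration of apnea/hypoxia episodes".

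On data capture, Section 3 says "Patient saturation is recorded every minute during the anesthetic on the electronic medical record and is available for review", and then "The duration and frequency of all measurements at or below 90% will be recorded by the Electronic Medical Record (EMR", closing the bracket.

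The sizing in Section 14 takes a 51% control rate and a 25-point difference and concludes that "the study would need a sample of 59 per group (total n = 118", again closing the bracket.

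No section says whether a duration belongs to an episode or to a patient, which patients enter the test, or what value is given to a patient who never desaturates. Duration is a listed outcome. It is not the primary objective or either numbered secondary objective in Section 1.

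**The concern.** An episode that did not happen has no length, so an analyst following Section 14 would ordinarily test only patients who desaturated. Desaturation is the event that Hypothesis 1 expects HFNC to prevent. Restricting the test to those patients selects on a post-randomisation outcome, and if the hypothesis is true the two subsets differ by design.

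The test could then report longer or shorter episodes on HFNC when the device altered no episode and only changed who had one. If HFNC mainly prevents short episodes, those left look long and the result goes against it. If it mainly prevents long ones, the result flatters it. Two analysts could also follow the same sentence and analyse different populations.

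**Working it through.** **1. Reproduce the plan's sample size.** Inputs from Section 14: p1 = 0.51, p2 = 0.51 − 0.25 = 0.26, power 80%, alpha 0.05. Sidedness is not stated; two-sided reproduces the figure. With mean proportion 0.385:

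n = [1.960·√(2·0.385·0.615) + 0.842·√(0.51·0.49 + 0.26·0.74)]² / 0.25² = (1.349 + 0.560)² / 0.0625 = 58.3, rounded up to 59 per group. This matches, and it is a per-patient calculation.

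**2. Who has a duration.** Salter 59 × 0.51 = 30.1; HFNC 59 × 0.26 = 15.3 (15.0 if the rate is exactly halved to 25.5%). Without an episode: 118 − 45.4 = 72.6, or 62%. If all 65 enrolled per group are analysed, the affected counts are 33.2 and 16.9.

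**3. Readings that the text allows.**
- One value per affected patient: about 30 v 15.
- One value per episode: the tested number is unknown, since episodes per patient are not given. Still only affected patients contribute, and repeated episodes in one patient are not independent.
- One value per patient, with zeros: 59 v 59 and no selection.

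**4. Mechanism.** Assumed, not from the documents: one exponential duration per affected patient, mean 2 min, and HFNC changes no episode's length. Salter mean total is 0.51 × 2 = 1.02 min.
- Prevention at random: HFNC total 0.26 × 2 = 0.52; mean among affected patients 0.52/0.26 = 2.0, equal to Salter.
- Half of prevention on the shortest episodes: HFNC total is 0.33 lower, 1.02 − 0.33 = 0.69; mean among affected patients 0.69/0.26 = 2.7. HFNC has fewer minutes in total yet appears to have longer episodes.

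**5. How often the affected-only test is significant.** 2,500 simulated trials per row, 59 per arm. Each HFNC episode is prevented with probability 1 − 0.26/0.51 = 0.49, at random or, for the stated share, only if it lies in the shortest or longest 49%.

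| Where prevention falls | Direction | t-test / Mann-Whitney |
|---|---|---|
| Random | against HFNC | 3% / 2% |
| Random | for HFNC | 2% / 3% |
| Quarter on shortest | against | 9% / 9% |
| Half on shortest | against | 20% / 25% |
| All on shortest (extreme) | against | 57% / 80% |
| Quarter on longest | for | 6% / 9% |
| Half on longest | for | 20% / 24% |
| All on longest (extreme) | for | 88% / 82% |

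Lognormal durations (mean 2 min, SD of log 0.8) at half share: 18% / 25% (shortest) and 16% / 24% (longest). With once-a-minute readings, in 1,000 trials, half on shortest falls to 12-17% / 14-22% and all on shortest to 24-47% / 35-72%.

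**6. Check of the replacement (total minutes, zeros included).** A percentile bootstrap interval for the mean difference has a half-width of about 0.5-0.6 min in the random and shortest-episode cases. It excludes zero in favour of HFNC in 48% (random), 22% (half shortest) and 8% (all shortest) of trials, and its coverage is 91-95%. Next, prevention is random and the remaining HFNC episodes are k times longer, so the HFNC mean total is 0.26 × 2 × k, against 1.02 on Salter:

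| k | HFNC mean total | Interval against HFNC | Rank test on totals favours HFNC | Affected-only t-test / Mann-Whitney detects lengthening |
|---|---|---|---|---|
| 1.96 | 1.02 | 2% | 62% | 57% / 43% |
| 2.5 | 1.30 | 8% | 54% | 83% / 66% |
| 3 | 1.56 | 15% | 51% | 92% / 79% |

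**The case against.** The best defence is that the affected-only reading is not compelled. The same sentence handles intervention counts, which have a natural zero, and speaks of comparing the two groups. Section 3 records the duration of all low readings, which fits cumulative time per patient. That stands: a reader might infer that the plan commits to testing only affected patients, and the text does not go so far. What it lacks is a rule.

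The consequence is also limited. No section says that HFNC selectively prevents short or long episodes, and if prevention is unrelated to length the error is nominal. The illustration uses continuous durations although saturation is recorded once a minute, which makes its rates somewhat high. Both points stand; the direction of the effect survives them.

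The most substantial objection is to the remedy. If HFNC really lengthened the episodes that remain, the affected-only t-test would show it in 57-92% of the simulated trials, whereas the interval for total minutes would do so in 2-15%. A reader might infer that the affected-only comparison should be dropped. It should not be: it carries information that total minutes lacks, provided it is not presented as a randomised comparison.

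**Conclusion.** The concern holds as a gap in definition with a real consequence on the ordinary reading. Section 14 plans a significance test on durations, and no section fixes the unit, the population or the value for patients without an episode. At the planned rates, the ordinary reading tests about 30 v 15 patients, selected by the primary outcome.

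The size of the error cannot be taken from the documents. It runs from nominal to large, in either direction, according to how prevention relates to length; about 20-25% false findings against HFNC is an illustration under assumed continuous exponential durations, not a prediction for this trial.

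A reader might infer that the trial's main conclusion is at risk. It is not: duration is a supporting outcome, and the primary comparison and sample size are untouched. Nor do the intervention counts share the problem. Section 14 also words the primary as proportions of episodes although its sizing is per patient; that is a separate point and adds no weight here. The change should be made, but it is not critical.

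**What to change.** In Section 14, replace the duration comparison with these elements:

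- **Measure:** total minutes with recorded SpO2 <90% during the anesthetic, which is the recording window in Section 3, for every randomised patient with saturation data. Score 0 only for a patient who was monitored and had no such reading; treat patients without data as missing. The plan expects 10% loss, so this distinction matters.
- **Analysis:** the between-group difference in means with one 95% interval method named in advance (for example, permutation-based). Wilcoxon-Mann-Whitney is supporting only and never read alone, because it can favour HFNC when HFNC's mean total is higher.
- **Affected patients:** duration with an estimate and interval, labelled as a non-randomised comparison.
- **Exposure:** monitored time by group, since total minutes depends on it and premature termination is a listed outcome.

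Before minutes are counted, reconcile the recording threshold in Sections 3 and 4 (90% or lower) with the definition in Section 1 and the Outcome Measures list (strictly below 90%).

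The cost is wording and one interval; the minute-by-minute data are already recorded. The downsides should be acknowledged. Total minutes is a different estimand that mixes incidence with length, and with about 49% (Salter) and 74% (HFNC) of values at zero it partly repeats the primary. It is imprecise at 59 per group and has little power to show that remaining episodes became longer, which is why the affected-only estimate is kept. The simulations used a percentile bootstrap, so the coverage of any other interval should be checked before it is adopted.

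### The test for desaturation duration and number of interventions is left open until the data are seen, ignores the randomization strata, and gives patients without an episode no stated place in the duration analysis

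*Combined protocol and SAP*

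**What the plan says.** Section 14 (Biostatistics) treats mean duration of desaturation episodes and number of interventions together. For the latter, "mean numbers of interventions to treat hypoxic events in the two groups will be compared using" either Student's t-test or the Wilcoxon-Mann-Whitney test. The only other text that bears on the choice is "Normality of the sample data will be assessed using normal quantile plots". The section does not expressly say that the plots decide the test. It gives no criterion, no default and no decision-maker, and does not say whether the plots are read blinded.

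Other places that matter:

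- **Status of the endpoints.** Section 1 makes the number of interventions the subject of Hypothesis 2 and the first secondary objective. Duration is in the Outcome Measures list of section 3 but has no hypothesis of its own.
- **When interventions can occur.** Section 3 tells anesthesia providers to act only once saturation is under 90%.
- **Strata.** Section 3 randomizes within STOP-BANG strata (5 or more v 4 or fewer). None of the tests in section 14 uses them.
- **Planning rates.** Section 14 says the cited study "reported a 51% incidence rate for desaturation episodes below 90% in patients with standard nasal cannula" and continues: "Thus to detect a difference of 25% with 80% power and a type 1 error rate of 0.05".
- **Patients with no episode.** No section says whether they enter the duration analysis as zero or are left out.

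**The concern.** A check of normality is useful only if its answer is in doubt. Here the planning rates settle it for the intervention count, because a patient who never desaturates should have no intervention. What the check does is postpone the choice of test until the outcome data are visible, with no rule to bind it. The two tests can disagree on data with many zeros, so the choice could decide whether Hypothesis 2 is declared supported.

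For duration, the plan leaves open something more basic than the test: which patients are in the comparison.

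**Working it through.** **1. Reproduce the sample size.** Inputs from section 14: control 51%, difference 25 points (so HFNC 26%), power 80%, alpha 0.05. Sidedness is not stated; two-sided is assumed. With pooled variance and mean rate (0.51 + 0.26)/2 = 0.385:

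n = [1.96·√(2·0.385·0.615) + 0.8416·√(0.51·0.49 + 0.26·0.74)]² / 0.25²
= [1.96·0.6882 + 0.8416·0.6651]² / 0.0625 = 3.642/0.0625 = 58.3, rounded up to **59 per group**, as stated. Power at 59 is 80.5%.

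**2. Share of zeros.** Control 1 − 0.51 = 49%, about 29 of 59. HFNC 1 − 0.26 = 74%, about 44 of 59 (74.5% for an exact halving to 25.5%). If the section 3 rule is followed, these patients have zero interventions. The same shares apply to duration only if patients without an episode are scored zero.

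**3. Would a normality check ever pass?** With the Shapiro-Wilk test as a stand-in for the plots, normality was rejected in every simulated arm for the count settings tried. In a further simulation (4,000 trials in each of six settings), the t-test was used only if both arms passed and Wilcoxon otherwise. Normality was accepted in none of the trials, so power (78-79%) and type I error (4.9-5.9%) were those of Wilcoxon alone.

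**4. Power of each test.** 59 per arm, two-sided 0.05, 10,000 trials per setting. The documents give no distribution among patients who desaturate, so a range is assumed. Here HFNC changes only the share who desaturate (51% v 26%):

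| Positive values | t-test | Wilcoxon |
|---|---|---|
| All equal | 81% | 81% |
| 1 + Poisson, mean 0.5 to 2 | 67-69% | 77-78% |
| Lognormal, SD 0.5 | 65% | 77% |
| Geometric, mean 2 or 3 | 52-56% | 78% |
| Exponential | 44% | 78% |
| 1 + negative binomial, mean 2, size 0.5 | 42% | 77% |
| Lognormal, SD 1.0 | 39% | 77% |
| Lognormal, SD 1.5 | 21% | 78% |

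If HFNC also lowers values among those who desaturate:

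| Positive values, control v HFNC | t-test | Wilcoxon |
|---|---|---|
| 1 + Poisson, total mean 2 v 1.5 | 92% | 89% |
| 1 + Poisson, total mean 3 v 2 | 97% | 92% |
| Geometric, mean 3 v 2 | 90% | 88% |
| Exponential, halved | 94% | 90% |
| Lognormal SD 1.0, halved | 86% | 91% |
| Lognormal SD 1.5, halved | 51% | 87% |

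Outside the planning rates, with 51% desaturating in both arms and exponential durations halved, the t-test has 53% power and Wilcoxon 14%.

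**5. Type I error.** With equal rates of 26% or 51% in both arms, counting a trial as positive if either test is significant gives about 6-8% in the settings where positive values vary. It stays near 5% when they are all equal.

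**6. Duration among patients with an episode only.** 59 × 0.51 = 30.1 and 59 × 0.26 = 15.3, so about 30 v 15. If HFNC prevents episodes without changing their length, the values follow the same distribution in both arms and power is about 5%, against about 79% with zeros included.

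**7. Strata.** In null simulations with STOP-BANG assumed prognostic, the unstratified rank test rejected in 3.4-3.8% of trials and the stratified one in 4.5-4.7%. Stratifying added about 1-3 points of power. The documents give no event rates by stratum, so these figures rest on that assumption.

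**The case against.** The strongest reply is that the plan, sensibly followed, does no harm. Naming two tests with a normality check is a conventional pairing, and on these data the check would point to Wilcoxon every time (step 3). This stands, and it limits the point. A reader might infer that the trial will use the t-test and lose tens of points of power, or that its false-positive rate is 6-8%. The documents support neither. The first needs someone to set the plots aside; the second needs both tests to be run and the better one reported, which section 14 does not describe. These are worst cases under the wording, not predictions.

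A reader might also infer that the planning rates alone make the t-test much weaker. They do not. The gap depends on an undocumented distribution and on HFNC changing incidence only; it disappears when all positive values are equal and can reverse by up to about 5 points when severity falls too.

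Nor do the documents support reading the 49% and 74% as zero shares for duration. A patient with no episode has no episode duration unless the plan assigns zero.

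Finally, with this many zeros Wilcoxon largely repeats the primary incidence comparison: across the incidence-only settings its power stays at 77-81%, close to the 80% planned for the primary test. This is a real cost of the remedy. What survives the objection is that the text binds no one to the sensible reading, and that the duration population is undefined.

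**Conclusion.** The point holds as a minor one on secondary endpoints; the primary test and the sample size are unaffected.

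For intervention counts, 49% and 74% zeros follow from the planning rates, provided the section 3 instruction is followed. Normality is then excluded in advance, and the check leaves only an open choice. Its consequence ranges from nothing to a loss of tens of points of power, with occasional small gains for the t-test, and at worst about 6-8% type I error. The power figures rest on assumed distributions.

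For duration, the gap matters more than the choice of test: without a rule for patients with no episode, the analysis could shrink to about 30 v 15 patients selected by an outcome that the treatment may affect. Leaving out the strata is a smaller loss, and its size depends on how prognostic STOP-BANG proves to be.

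**What to change.** In section 14, drop the normality check for these two endpoints and pre-specify one analysis: a rank-sum test stratified by STOP-BANG score at randomization (van Elteren, with tie correction) on each patient's total duration of desaturation and total number of interventions, counting zero for patients without an episode. Show beside it the mean difference with a bootstrap confidence interval. Medians alone would say little: in one count setting (1 + Poisson, mean 1) the control median was zero in 44% of simulated trials. Duration among patients with an episode can be described, but not tested as a randomized comparison.

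The cost is a sentence or two in the plan, with no new data and no change in sample size. The downside is that the rank test gives no difference in means, largely overlaps with the primary incidence comparison, and is weak if HFNC shortens episodes without preventing them. If the sponsor expects mainly a severity effect, a pre-specified count or two-part model would also close the choice. The essential step is to fix one method per endpoint before the outcome data are seen by arm, including at the interim analysis.
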